Overall palbociclib treatment will be summarized as below for the FAS overall and by LOT:

- Number of cycles of palbociclib received
- Length of palbociclib treatment (months)
- Treatment disposition: (still receive palbociclib, discontinued palbociclib)

Palbociclib prescribing and treatment patterns will also be explored by cycle. For each cycle, below will be summarized:

- Starting dose (if less than 125mg, present reason)
- Primary reason for selecting palbociclib for the first cycle
- Dose modification (type, dose received after modification, reason)

Treatment patterns following enrollment will be reported, which include only lines started at enrollment:

- Type of therapy received (such as chemotherapy, hormonal therapy, other therapy)
- Agent (drug) composition of the treatment regimen received
- Time from initiation of treatment to initiation of each subsequent lines of treatment

- Time from discontinuation of previous line to initiation of the subsequent line of treatment
- Time from the start to end of each treatment line (in months for the total duration). This measure will be presented overall and by the top four regimens received in the line.

The sequence of agents/combination regimens received for first-line treatment in the ABC/MBC setting and subsequent lines of treatment will be presented. The proportion of all patients with each unique sequencing pattern will be reported for the overall study sample. Type of therapy sequencing (e.g., endocrine only, chemotherapy only, endocrine therapy combined with target therapy) will also be presented in the same format.

CLINICAL OUTCOMES

rwTR, rwPFS, and OS will be assessed by LOT (1st line, \geq 2nd line) in the ABC/MBC setting for the FAS. Based on the nonrandomized, observational nature of the study design, no clinical endpoints will be separately assessed and compared between specific treatment regimens.

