Real-world tumor response (complete response, partial response, stable disease, progressive disease) is determined by physician based on imaging, biopsies, biomarkers, and/or clinical judgment. Response as assessed by Response Evaluation Criteria in Solid Tumors (RECIST) criteria may not be available for all patients. rwTR will be derived as the best tumor response recorded from the palbociclib combination treatment start date until the first documentation of progressive disease. Only response assessments recorded on or before the start date of next subsequent line of treatment will be considered. The proportion of patients with a best response of complete response, partial response, stable disease, and progressive disease will be calculated and reported. Real-world response rate is defined as the proportion of patients with a best tumor response of complete response or partial response. Best tumor response, clinical benefit, and study end date are defined in Appendix 1 Data Derivation Details.

rwPFS will be estimated by LOT in the ABC/MBC setting. rwPFS is defined as time (months) from initiation of the palbociclib combination treatment to the earliest of clinician-documented progression or death due to any cause, whichever occurs first. Patients absent of the above events will be censored at the last date of response assessment without progressive disease.

OS will be estimated by LOT in the ABC/MBC setting. OS is defined as time (months) from initiation of the palbociclib combination treatment to date of death due to any cause. Patients do not have a documented death will be censored at last available visit date known to be alive.

Follow-up time will be calculated as time (months) from initiation of the palbociclib combination treatment to date of death or last available visit date. Median follow-up time and range (minimum, maximum) will be provided overall and by LOT.

Time-to-event outcomes (i.e., rwPFS, OS) will be analyzed using the Kaplan-Meier method and estimated survival curves will be displayed when appropriate. The number of patients at risk over time will be presented. A summary table will include number of patients with events, number of patients censored, and Kaplan-Meier quartiles (when estimable) accompanied by two-sided 95% confidence intervals (CIs). Based on the Kaplan-Meier life table, Survival function estimates at the specific time points (eg, 6, 12, 18, 24, 30 and 36 months) will also be reported along with two-sided 95% CIs.

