Palbociclib Hormonal Partner: the concurrent hormonal therapy recorded while on Palbociclib. If the patient took both LETROZOLE and ANASTROZOLE then the first hormone partner (chronologically) is assigned.

Time from Initiation of Treatment to Initiation of Each Subsequent Line of Treatment: defined in days by subtracting the date of treatment initiation from the date of initiation of each subsequent treatment line and adding 1.

Time from Discontinuation of Previous Line to Initiation of the Subsequent Line of Treatment: defined in days by subtracting the initiation date of the previous line from the initiation date of the subsequent line and adding 1.

Time from the Start to End of Each Treatment: defined in months by subtracting the discontinuation date from the initiation date for each treatment line, adding 1, and then dividing by 30.4.

Charlson Comorbidity Index:

Assign a point score to each condition per Table 5 below. Point scores are then summed within patient to generate an overall score of disease burden.

Table 5: List of Comorbidities Collected at Time of Enrolment

Condition	Point Score
Charlson Comorbidity Index conditions:	
Cerebrovascular disease	1
Chronic pulmonary disease	1
Congestive heart failure	1
Connective tissue disease	1
Dementia	1
Diabetes with end organ damage	2
Diabetes without end organ damage	1
Depression	1
Hemiplegia or paraplegia	2
History of myocardial infarction	1
HIV/AIDS ^[a]	6
Hypertension	1
Mild liver disease	1
Moderate to severe liver disease	3
Use of warfarin	1
Moderate to severe renal disease	2
Peptic ulcer disease	1
Peripheral vascular disease	1
Skin ulcers/cellulitis	2
Other specific comorbidities	
Leukemia	N/A
Lymphoma	N/A
Neutropenia	N/A
Anemia	N/A
Other comorbidities not listed above	N/A
No comorbidities	N/A

[a] AIDS = acquired immune deficiency syndrome; HIV = human immunodeficiency virus.

PFIZER CONFIDENTIAL

ECOG Performance Scale:Developed by the Eastern Cooperative Oncology Group, [name], Group Chair.*

Grade	ECOG PERFORMANCE STATUS
0	Fully active, able to carry on all pre-disease performance without restriction
1	Restricted in physically strenuous activity but ambulatory and able to carry out work of a light or sedentary nature, e.g., light house work, office work
2	Ambulatory and capable of all selfcare but unable to carry out any work activities; up and about more than 50% of waking hours
3	Capable of only limited selfcare; confined to bed or chair more than 50% of waking hours

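### The SAP gives no censoring rule for treatment-line timing; taken as derived, time to next line counts only starters and line duration only ended lines, which biases long durations short

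*SAP*

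**What the plan says.** SAP Section 8, Study Drug Exposure, lists among the treatment patterns "Time from initiation of treatment to initiation of each subsequent lines of treatment" and "Time from the start to end of each treatment line (in months for the total duration"), the latter overall and by the four most frequent regimens in the line. The same subsection reports "Length of palbociclib treatment (months") and a disposition split into "still receive palbociclib, discontinued palbociclib", so ongoing treatment is expected.

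Appendix 1 derives time to next line by "subtracting the date of treatment initiation from the date of initiation of each subsequent treatment line" and line duration by "subtracting the discontinuation date from the initiation date for each treatment line". It names no substitute date when the second date does not exist. Under General Methods, continuous variables are summarised by mean, SD, median, range and a missing count.

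Clinical Outcomes states that "Time-to-event outcomes (i.e., rwPFS, OS) will be analyzed using the Kaplan-Meier method" and gives censoring rules for those two endpoints only. The Kaplan-Meier sentence in protocol Section 8.7 names death as an example; it would permit the method here but does not assign it.

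**The concern.** Prescribing and treatment patterns are the primary goal in protocol Section 8.1, and treatment sequence is a listed objective. In a descriptive study the reported durations are themselves the result, so the absence of a hypothesis test does not make their bias harmless.

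Patients whose line has ended by the cut-off, or who have already started the next line, are disproportionately those who stopped early. A plain median over them is therefore short, and more so the longer the true duration. Contrasts between first and later lines shrink as a result.

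Because no rule is stated, two competent programmers could report about 16 or about 25 months from the same data.

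**Working it through.** **Does nearby text supply a rule?**

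- SAP Section 7 imputes partial dates. An ongoing line has no stop date to complete.
- The General Methods formula for elapsed time needs two dates and gives no end date for an ongoing line.
- Appendix 1 defines a study end date but uses it only for study duration.
- The restriction "which include only lines started at enrollment" selects lines; it does not say how an incomplete one is treated.

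So time to next line can take a value only in starters. Line duration has a value only for ended lines, unless the programmer supplies a truncation date. Length of palbociclib treatment can be read as observed exposure or as time to discontinuation.

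**Inputs for the size.** The plan states no figure for line timing, so there is none to reproduce. From the documents:

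- data collection from 16 December 2016 to 16 December 2021, i.e. c = 60 months (protocol Section 5);
- PFS medians of 24.8 and 9.2 months (protocol Section 6.2), used as proxies for time on a line.

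Assumed: a middle median of 15 months, exponential durations, and uniform accrual over a = 24 (36) months.

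**Share still ongoing at cut-off.** With λ = ln 2 / m:

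q = [exp(−λ(c−a)) − exp(−λc)] / (λa)

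For m = 24.8 and a = 24: λ = 0.02795, so q = (0.3656 − 0.1869) / 0.6708 = 0.266.

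**Ended-only median.** This solves P(T ≤ t and ended) = (1 − q)/2. For t ≤ c − a the left side is 1 − exp(−λt), which gives

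t = m × [1 − log₂(1 + q)]

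For m = 24.8 and a = 24: 24.8 × (1 − log₂ 1.2664) = 24.8 × (1 − 0.3407) = 16.35.

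Under the exponential assumption the proportional shortfall is log₂(1 + q). It is 14% when 10% are ongoing and 38% when 30% are.

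**Truncation instead.** If ongoing lines are cut at the cut-off, with follow-up f, the median solves exp(−λt)·P(f > t) = 0.5 and the mean is the integral of that product.

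| True median | Ongoing, a = 24 (36) | Ended-only median | Truncated median | Truncated mean | True mean |
|---|---|---|---|---|---|
| 24.8 | 27% (32%) | 16.4 (14.8) | 24.8 (24.4) | 26.2 (24.2) | 35.8 |
| 15 | 11% (16%) | 12.7 (11.8) | 15.0 (15.0) | 19.2 (18.2) | 21.6 |
| 9.2 | 3% (6%) | 8.8 (8.5) | 9.2 (9.2) | 12.9 (12.5) | 13.3 |

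In simulation, Kaplan-Meier with ongoing lines censored returns the true medians to within 0.1 month. The true difference between the longest and shortest case is 24.8 − 9.2 = 15.6 months; ended-only it is 16.4 − 8.8 = 7.6 (14.8 − 8.5 = 6.3).

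**Time to next line.** Add an assumed exponential gap with mean 1 month, and let the chance of dying without a next line be independent of time on the line. Starters-only medians against those under complete follow-up are:

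- 17.1 (15.6) against 25.8;
- 13.6 (12.7) against 16.0;
- 9.8 (9.5) against 10.2.

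**Interim at month 36, a = 24.** Ended-only medians are 9.8, 8.6 and 6.9; truncated medians are 16.8, 13.6 and 9.2.

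**The case against.** The strongest reply is that ended-only is one of two readings for line duration. Under truncation at last contact the final medians are essentially right, and only the means stay short. That is correct, but the SAP does not choose between the readings. For time to next line, truncation is not available as derived.

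Second, protocol Section 8.1 plans about 3 years of follow-up after each patient's last palbociclib. If that were met, nearly all palbociclib lines would have ended by the final analysis, apart from withdrawals and deaths on treatment. Under the assumptions above, however, a 60-month window leaves room for 3 years after treatment in only 27% (18%) of patients when the median is 24.8, and 54% (36%) when it is 9.2. The two plans pull in opposite directions, so the illustration is conditional.

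Third, SAP Section 4 limits longitudinal endpoints at an interim to patients with enough follow-up. It does not define enough, so this softens the interim figures without removing the problem. They are upper illustrations.

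Fourth, missing counts, treatment disposition and follow-up time are reported. These make immaturity visible but do not correct the durations. Observed exposure and a starters-only gap are legitimate descriptions if labelled as such.

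A reader might also compare starters with the cumulative incidence over all patients and call the whole gap bias. The documents do not support that, because part of the gap is the change of denominator once deaths without a next line are kept. Like for like, the share of starters who begin by month 24 is 65% (71%) against 47% under complete follow-up for a median of 24.8, 74% (79%) against 65% for 15, and 85% (88%) against 82% for 9.2.

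**Conclusion.** The point holds as a gap in the estimation rule. Followed as derived and summarised, the SAP gives starters-only and ended-only figures on a primary-goal measure. Under the stated assumptions the ended-only median falls short by 34% (40%) at 24.8 months, 16% (21.5%) at 15 and 4% (8%) at 9.2. Starters-only time to next line is short by a similar proportion in the longest and shortest cases: 34% (40%) and 4% (8%).

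Two stronger readings go too far. One might infer that the SAP states a restriction to starters and ended lines; it does not, and the restriction follows only from the derivations. One might also infer that line durations would be seriously wrong throughout; short durations at the final analysis are little affected, and truncated final medians are nearly right.

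The direction is firm. The size rests on assumed accrual, exponential shape and PFS medians standing in for time on a line. No test or sample size is affected.

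**What to change.** In SAP Section 8 (Study Drug Exposure and Clinical Outcomes) and Appendix 1:

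- Estimate the duration of each line and the time to palbociclib discontinuation by Kaplan-Meier. Define the event as the end of the line for any reason, including death on treatment. Censor patients without the event at the last date known to be on that line. Report the median with 95% CI and the number ongoing.
- Patients may already be on palbociclib at consent (protocol Table 1, note 8). For them, use delayed entry at consent or report them separately; otherwise Kaplan-Meier from initiation would be biased long.
- Report time to next line over all patients who started the index line, as cumulative incidence with death before a next line as a competing event.
- Keep observed exposure or a starters-only summary if wanted, labelled as such and with its denominator.

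The cost is SAP wording and a few tables. Some medians may not be reached at early interims. Censoring dates for lines after palbociclib may be sparse, because data are then entered only when a new regimen is prescribed and at end of study (protocol Table 1, note 2).

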Participation in this study is not intended to change the routine treatment patients receive, as determined by their prescribing physicians; all treatment decisions, type, and timing of disease monitoring are at the discretion of the treating physician and patient. Assessments include patient questionnaires and quality of life (EORTC QLQ-C30, G8 Screening Tool,

PFIZER CONFIDENTIAL

Activities of Daily Living [ADL] Questionnaire), site questionnaires, physician metastatic breast cancer (MBC) treatment selection survey, and **CCI** [REDACTED].

Baseline (or Visit 1) is defined as the date of study enrolment when informed consent is obtained and inclusion/exclusion criteria assessed. The Data Entry Schedule is included in Table 1 and the EORTC QLQ-C30 and Geriatric Assessments in Table 2.

Table 1: Data Entry Schedule

Data Collection and Entry ¹	►	Baseline	During Treatment with Palbociclib	Post Treatment with Palbociclib
		SOC Visit 1	SOC Visit 2 through End of Treatment with Palbociclib	Follow-up through End of Study ²
Informed Consent & Inclusion/Exclusion Criteria		x		
Patient Demographics, Study Site Characteristics, Medical History, Baseline Concomitant Medications, Baseline Metastatic Disease Status		x		
Breast Cancer Diagnosis and Recurrence History		x		
Breast Cancer Treatment ³		x ³	x ³	x ³
Physician MBC Treatment Selection Survey ⁴		x ⁴	x ⁴	x ⁴
Performance Status (ECOG)		x	x	
Clinical Assessments ⁵		x ⁵	x ⁵	x ⁵
CCI				
Laboratory: CBC ⁷		x ⁷	x ⁷	
Adverse Events and Serious Adverse Events ⁸		x ⁸	x ⁸	

SOC = Standard of care; ABC = advanced breast cancer; CBC = complete blood count; ECOG = Eastern Cooperative Oncology Group; MBC = metastatic breast cancer; SAE = serious adverse event

1. Data is collected in accordance with normal standard of care visits, enter all data available per Data Entry Schedule into the electronic data capture system.

2. Follow up through End of Study: Enter data at SOC visits where each subsequent (post palbociclib treatment) MBC treatment regimen is prescribed and at end of study.

3. Breast cancer treatment: including surgery, radiation, systemic chemotherapy, hormone therapy, and/or targeted therapy, in both neoadjuvant/adjuvant and metastatic disease settings, prior to, during, and post palbociclib treatment; supportive care is also collected in the metastatic setting while on this study.

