5 ANALYSIS SETS

FULL ANALYSIS SET

The full analysis set (FAS), also referred to as the Safety Analysis Set (SAS), or quality of life analysis set (QoLAS), is defined as all subjects enrolled in the study and received at least one dose of study medication. The FAS will be used in all analyses unless specified otherwise.

PER-PROTOCOL ANALYSIS SET

The per-protocol analysis set (PPAS) is a subset of the FAS and defined as all subjects enrolled in the study who a) received at least one dose of palbociclib, b) did not have any treatment-free interval (see Appendix 1 Data Derivation Details) and c) had no disease-free interval (see Appendix 1).

CCI

SUBGROUPS

Key measures, such as baseline patient characteristics, comorbidities, prior breast cancer treatments, treatment regimens during and after palbociclib treatment, and clinical outcomes will be assessed for the FAS and by specific subgroups defined by palbociclib hormonal partner and up to two additional subgroups. Patients will be classified into one of two or more levels for each subgroup of interest.

Potential subgroups of interest include:

- Age at enrolment (≥ 70 years / < 70 years)
- Ethnicity (Hispanic or Latino / Not Hispanic or Latino)
- Receipt of prior endocrine treatment (yes / no)
- Eastern Cooperative Oncology Group (ECOG) performance status (0-1 / 2-4)
- Insurance type (public / private / uninsured)
- ABC/MBC diagnosis at enrolment (de novo / recurrent disease)
- Disease stage at initial diagnosis (stage 0-IIIA / stage IIIB-IV)
- Charlson Comorbidity Index (CCI) (0 / 1-2 / 3+)

PFIZER CONFIDENTIAL

- Type of regimens (endocrine only / chemotherapy only / endocrine therapy combined with target therapy)
- Disease-free interval (0-<12 months / 12-<24 months / 24-<36 months / 36+ months)
- Visceral disease at enrolment (yes / no)
- Menopause status (yes / no)
- Line of therapy (LOT) in the ABC/MBC setting (1st line, ≥2nd line]

PFIZER CONFIDENTIAL

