8 STATISTICAL ANALYSIS

This study has a convenience sample; thus, results may not be generalizable to the entire population with the disease. Due to the study's exploratory nature, study measures will be summarized descriptively. Furthermore, any p value reporting should be placed in a descriptive framework for hypothesis generation and any such inferential analysis is intended to guide further research.

All analyses will be conducted using SAS® version 9.4 or higher.

The intention is to analyze all available data. In the advent that COVID may cause gaps in subject data or require adjustments to statistical methodologies, our intent is to address such issues if or as needed. Both ICON and Pfizer have internal guidances and recommendations on file to assist with decision-making with regards to COVID-related data issues and these will be consulted if or as needed.

GENERAL METHODS

For continuous variables, means, standard deviations (SD), medians, minimums, maximums, and missing will be reported. For discrete variables, frequencies and percentages will be reported. Missing or unknown categories for each variable also will be presented. Percentages will be calculated excluding missing or unknown values. 95% Confidence Intervals (CI) are two-sided.

All summaries will be performed for all patients in the corresponding analysis set and by treatment combination defined at study entry within the corresponding analysis set:

- Palbociclib + Letrozole or Anastrozole
- Palbociclib + Fulvestrant
- Palbociclib + Exemestane
- Other

The baseline record is defined as the last observed measurement prior to palbociclib administration. Change from baseline is defined as the post-baseline value minus the baseline value.

Time in days between two dates will be calculated using the formula most recent date minus earlier date plus 1. For time in months, the same formula for days will be applied but then divided by 30.4. For time in years, the same formula for days will be applied but then divided by 365.25.

Variable definitions are found in Appendix 1 Data Derivation Details.

DISPOSITION OF SUBJECTS

A subject disposition summary will be reported. Subjects' study completion date and reason for premature termination will be reported in listing format. Number of subjects with initial diagnosis and with recurrent diagnosis will be reported in table and listing format.

DEMOGRAPHIC AND BASELINE CLINICAL CHARACTERISTICS

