Cox proportional hazards models may be developed for each time-to-event outcome when appropriate. These models would include covariates such as age, comorbidities, and hormonal partner. If performed, the validity of the proportional hazards assumption will be assessed using plots of scaled Schoenfeld residuals versus time as well as score tests for each covariate in each model. If necessary, alternative Cox modeling approaches (e.g., parametric models, restricted mean survival time, stratification, time-varying covariates) will be considered if there is evidence of nonproportional hazards. Hazard ratios for each model term, along with two-sided 95% CIs, will be computed and displayed in a table for each covariate in the final model for each outcome.

SAFETY ANALYSES

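### OS and rwPFS are counted from first palbociclib dose, so any patient enrolled after that dose brings guaranteed survival time into the risk set, and no delayed-entry or new-starter analysis is planned

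*SAP*

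**What the plan says.** SAP Section 8, Clinical Outcomes, sets the time origin: "OS is defined as time (months) from initiation of the palbociclib combination treatment to date of death due to any cause", and "rwPFS is defined as time (months) from initiation of the palbociclib combination treatment". Follow-up time starts at the same point. The estimator is ordinary Kaplan-Meier ("Time-to-event outcomes (i.e., rwPFS, OS) will be analyzed using the Kaplan-Meier method") with right-censoring rules only. The section adds "The number of patients at risk over time will be presented" and "Cox proportional hazards models may be developed for each time-to-event outcome when appropriate". The alternatives to the Cox model are reserved for non-proportional hazards.

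Study entry is a different date. SAP Section 3, Study Design: "Baseline (or Visit 1) is defined as the date of study enrolment when informed consent is obtained".

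The population is the full analysis set (SAP Section 5: "The FAS will be used in all analyses unless specified otherwise"), meaning everyone enrolled with at least one dose. The per-protocol set is restricted by treatment-free and disease-free intervals, not by whether treatment began after consent.

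The safety-reporting clause starts the reporting period at consent for a patient who is already on palbociclib. It appears in Protocol Section 10 (Reporting period) and in footnote 8 to Table 1 of both documents. Protocol Sections 8.2.1 and 8.2.2 neither exclude such a patient nor cap the time since first dose.

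**The concern.** A patient who starts palbociclib and enrols later is observed only because she lived long enough to consent. Anyone who died in that interval is not in the data. This is left truncation. Counting the interval as time at risk adds person-time in which a death could not have been recorded, so early survival is overstated and the whole curve is lifted. For rwPFS the interval is probably mostly progression-free as well, though no criterion requires it.

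OS and rwPFS by line of therapy are the planned time-to-event outcomes. Any distortion is relatively larger where the median is short, so lines of therapy could be affected unequally. The number-at-risk table would carry the same error. If 10% or 30% of 1500 were such patients, 150 or 450 would be shown at risk at month 0 although they had not yet enrolled.

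**Working it through.** There is no plan figure to reproduce, because the point concerns the definition of the risk set. The check has two parts: whether any text corrects for late entry, and how large the effect could be.

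**1. Text.** The visible text mentions no entry time, no risk set opening at consent, no new-starter subset and no subgroup by timing of first dose. The one related limit, in SAP Section 8 (Study Drug Exposure), confines the treatment-pattern summaries to lines begun at enrolment; it does not reach OS or rwPFS. Part of SAP Section 5 is blacked out, so this rests on what can be read.

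**2. Inputs.**
- Medians *m*: 9.2 and 24.8 months, the trial PFS medians quoted in the background of both documents; 40 months is assumed for OS.
- Share exposed at consent *q* and mean lag *L*: not in the documents, so assumed. Lag is uniform on (0, 2*L*).
- Hazard shape *k*: assumed; Weibull 1.5 (rising), 1 (constant), 0.8 (falling).

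**3. Formula.** With S(t) = exp[−ln 2 · (t/m)^k], the planned Kaplan-Meier estimates

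(1 − q)·S(t) + q·E[P(T > t | T > lag)]

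and the naive median is where this equals 0.5. For a constant hazard λ = ln 2/m and t ≥ 2L, the median shift is

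ln(1 − q + q·M)/λ, with M = (e^{2Lλ} − 1)/(2Lλ).

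**4. Worked case, q = 30%, L = 3, k = 1.**
- m = 9.2: λ = 0.0753, 2Lλ = 0.452, M = 1.264, 1 − q + qM = 1.0793, shift = ln(1.0793)/0.0753 = 1.01 months.
- m = 24.8: λ = 0.02795, M = 1.0887, 1 − q + qM = 1.0266, shift = 0.94 month.

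**5. Median shift in months** (share and lag defined among enrolled patients):

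| Share, mean lag | Hazard | m = 9.2 | m = 24.8 | m = 40 |
|---|---|---|---|---|
| 10%, 1 month | rising | +0.03 | +0.02 | +0.01 |
| | constant | +0.10 | +0.10 | +0.10 |
| | falling | +0.20 | +0.24 | +0.26 |
| 30%, 3 months | rising | +0.42 | +0.24 | +0.19 |
| | constant | +1.01 | +0.94 | +0.92 |
| | falling | +1.58 | +1.77 | +1.91 |

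If share and lag are defined before selection, the 30%, 3-month figures at 9.2 fall to as low as +0.35, +0.8 and +1.2 (rising, constant, falling). At 30% and 3 months, 6-month survival rises by 2.8 to 6.0 points at median 9.2 and by 0.9 to 3.2 points at 24.8, over all shapes and definitions. If only half of the exposed patients were selected for being progression-free (q = 15%), the rwPFS shift at 9.2 is +0.2, +0.5 and +0.8.

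**6. Does delayed entry remove it?** Simulation with n = 1500, 25% exposed, fixed lag of 3 months and constant hazard gave these medians (naive / delayed entry / new starters only): 10.02 / 9.20 / 9.19 for a true 9.2, and 25.57 / 24.79 / 24.81 for a true 24.8. When lag is independent of prognosis, both alternatives recover the truth.

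**7. If late enrollers have a worse prognosis** (30%, mean lag 3, constant hazard; naive / delayed entry / new starters):
- 1.25 times the hazard: 9.7 / 8.7 / 9.2 and 24.1 / 23.3 / 24.8.
- 1.5 times: 9.25 / 8.3 / 9.2 and 22.9 / 22.0 / 24.8.

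The naive median still exceeds the delayed-entry median of the same patients by 0.8 to 1.0 month on these rounded figures, but against new starters it can be too high, about equal or too low.

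**The case against.** The best defence is that the study means to enrol new starters. Questionnaires are due before palbociclib begins, the physician survey is tied to the start of therapy, and "The baseline record is defined as the last observed measurement prior to palbociclib administration". Study Day counts from the consent date, and the early blood-count windows at Days 15, 21 and 28 make most sense if first dose falls near consent. The contrary evidence is one safety clause, repeated. This stands as a reason to expect few late enrollers and short lags. It does not close the gap: those passages set collection times and derivations, not eligibility, and they conflict with a clause that expressly foresees exposed patients.

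The second objection is noise, and it partly stands. At median 9.2 with all 1500 patients, the SD of the estimated median is 0.34 month, so a 1-month shift is about three SDs. Results are planned by line of therapy, however. In an assumed stratum of 1050 with median 24.8 the SD is 1.09, and only the falling-hazard shift at 30%, 3 months exceeds it. In an assumed stratum of 450 with median 9.2 the SD is 0.63, and the rising-hazard shift is below it. In many settings the bias would therefore be smaller than sampling error.

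Third, the study is descriptive, uses a convenience sample and has treatment patterns as its primary goal. That lowers the stakes, but medians and landmark survival are themselves the planned descriptive output.

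Finally, delayed entry is not always nearer the new-starter median: at 1.5 times the hazard and median 9.2, the naive value is closer. That closeness comes from two errors cancelling, which is a reason to show both analyses.

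**Conclusion.** The concern holds. For any patient enrolled after first dose, the stated rule counts time in which death could not have been observed as time at risk, and nothing visible in the plan corrects it. How much this matters cannot be settled from the documents. The bias is nil with no late enrollers, negligible at 10% and 1 month, and about 1 month in the median at 30% and 3 months under a constant hazard (5%, 11% and 17% of a 9.2-month median for rising, constant and falling hazards; 1%, 4% and 7% of 24.8). These figures assume that lag is independent of prognosis; if late enrollers do worse, the sign relative to new starters can reverse. Because the plan reports neither the share nor the lag, a reader of the results could not tell which case applies. The change should be made; confidence that the bias is material in this study is moderate at best.

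**What to change.** 1. Reconcile the passages that assume enrolment before first dose with the clause that provides for patients already exposed at consent.
2. Report the number enrolled after first dose and the distribution of their lag, overall and by line of therapy. If there are none, nothing else changes.
3. Otherwise keep palbociclib start as the time origin, but enter each patient into the risk set at the later of first dose and consent in the Kaplan-Meier analysis, the number-at-risk table and any Cox model. State the assumption that entry lag is independent of prognosis.
4. For rwPFS, count and list patients whose progression precedes consent; they contribute no time at risk.
5. Add a sensitivity analysis of patients enrolled on or before first dose, shown beside the delayed-entry result. A gap between the two is a check on the assumption in step 3.

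The cost is SAP wording and an entry time in the survival code; the first-dose and consent dates are already required. Some precision is lost. The SD of the median at 30%, 3 months (naive / delayed entry / new starters, constant hazard) is 0.34 / 0.35 / 0.41 with 1500 patients at median 9.2, 0.63 / 0.64 / 0.73 with 450 at 9.2, and 1.09 / 1.09 / 1.29 with 1050 at 24.8. In a stress case of 50% and 6 months, which the documents do not suggest, it is 0.34 / 0.40 / 0.49 with 1500 at 9.2, so the loss is no longer small.
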